After obtaining informed consent, baseline data will be obtained in person prior to the initiation of treatment. Participants will meet with the research assistant to complete the computer-based conjoint analysis tasks. Patient identifiers will be removed to maintain data confidentiality. Only the PI will have access to the master files. For conjoint analysis, each participant will be asked to express his preference for attributes and attribute levels for active surveillance and five active treatments for clinically localized PCa (RP, RALP, EBRT, PT, BT) based on choice sets presented. The choices will vary based on the differing attributes of various treatments ascertained in prior work and focus groups. After pilot testing and refining the conjoint task in Phase 1, final attributes and levels will be used. Trade-offs among treatment features will be calculated in patient-specific utilities or part-worths associated with the attribute levels in the study. For other outcomes, participants will receive the following surveys via mail within 1-2 weeks after enrollment and prior to treatment initiation: SF-36, EPIC, AUA-SI, regret scale, CES-D, MAX-PC, SWD, PSQ-18, CPS, DCS and trust scale. Demographics, health and family history, clinical covariates and cancer progression data will be collected at 3, 6, 12 and 24 month follow-up. Histological tumor grade Gleason score and PSA and annual Elixhauser comorbidity score [257-258] will be obtained from the Pennsylvania Integrated Clinical and Research Database (PICARD), a UPHS, Fox-Chase Cancer Center electronic database, and PVAMC administrative and patient HER database. Retention and survey administration: During enrollment, importance of active participation will be emphasized. All participants will complete self-administered surveys at baseline within 1-2 weeks after enrollment (prior to treatment initiation) and again 3,6,12 and 24 months post-enrollment (see Appendix for copies of instruments, consent and medical chart review form). Non-respondents will be contacted via telephone after 10 days. In case of non-response due to death, cause of death will be noted and the physician investigators will determine cause of death (PCa or non-PCa related). The PCa conjoint analysis task, DCS, CPS and trust scale will be administered at baseline only, immediately after diagnosis of PCa and before treatment decision. Procedure for Data Sharing and Modification coordination: In Phase-1 on the study, data will be generated from focus group meetings that will take place on Penn campus. Focus group data will not be shared with other sites. This data will be used to generate a conjoint analysis instrument. This conjoint analysis instrument will be administered to participants in the intervention arm at all three sites during the Phase-2 of the study. The paper copies of various instruments that all participants complete will be stored at Penn campus in a secure office. In addition, clinical data obtained through chart abstraction will also be stored at Penn campus in a secure office. All electronic data bases will be pass word protected and only the study personal will have access to this data. Raw data will not be shared with other sites, only results in aggregate format with de-identified information will be made available to other sites. Each site PI will be responsible for addressing modifications. Additionally, the Penn site PI [name] will have overall responsibility of tracking all modifications. In case of a reportable event at a site, the site PI will inform Penn IRB and Penn site PI regarding the reportable events. Additionally, during Phase-1 of the study, we will conduct audio/video recording of focus group meetings.

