
The following documents are currently attached to this item:

There are no documents attached for this item.

Analysis Plan

Analytic Methods General: The statistical analysis will proceed in three stages: First, we will check the data quality and carry out descriptive analyses of demographics and key outcome variables. Next, we will assess preferences using conjoint analysis and inferential analysis. For continuous outcome variables, we will check for homogeneity of errors using spread-vs.-level plots and will consider transforming variables that either are highly skewed or have variance that depends strongly on the mean. We will use methods based on general linear model (univariate and repeated-measures ANOVA, mixed models) to analyze uncensored continuous outcomes, such as generic and prostate-specific HRQoL, psychological wellbeing and satisfaction with care. For potentially censored outcome variables such as time to PSA recurrence, we will use Kaplan-Meier curves and Cox proportional hazard models. Poisson regression (zero-inflated) will be used for count data. We will use Bonferroni correction for multiple testing. We will use propensity-score and instrumental variable approach to minimize observed and unobserved bias within groups (i.e. intervention group and usual care control group). **Missing Data:** We will attempt to prevent missing data by ensuring that data collection is as complete as possible. Should there be substantial missing data, however, we will employ analysis and imputation methods to reduce bias and increase efficiency [279-282]. Based on the proportion of missing data, we will use complete-case analysis, or explore available techniques, such as standardized score imputation, simple means imputation, maximum likelihood model-based imputation, data augmentation, etc. [281]. When data are evidently non-missing at random, we will conduct explicit non-ignorable modeling and sensitivity analysis [278]. **Propensity score matching:** In observational studies, comparisons between treatment groups that do not adjust for factors associated with treatment choice may be biased. Propensity score technique offers a highly practical approach to address such bias [283]. Here, the probability of each participant being in the treatment arm (i.e., the propensity score), is estimated. Participants are sorted by their propensity scores; the sample is divided into strata based on estimated scores, the treatment effect within each stratum estimated and overall estimate computed by aggregating across strata in a weighted analysis. When the model for predicting treatment status includes all relevant covariates, within strata treatment groups will be balanced on all predictors and the overall comparison of treatment arms will have substantially lower bias. We will use a model relating PCa treatment (RP, RALP, EBRT, PT, BT or AS) to baseline factors [283-284]. To study the extent to which treatment groups are now matched, we will compare t-statistics for these covariates before and after adjusting for propensity score. This will be done separately for intervention group and usual care controls. **Instrumental variable analysis:** Another limitation of observational research is the strong potential for confounding bias, due to differences in comparison groups that are not reflected in the data (i.e., unobserved bias). The instrumental variable (IV) approach is useful in reducing this bias. This technique uses one or more observable factors that influence outcome only indirectly (the IV). This allows one to mimic randomization with different likelihoods of receiving a particular treatment [227, 285-291]. Physicians play an important role in patients treatment choice- a majority of the PCa patients report that their physicians recommendation was the most important factor in their treatment choice [11-12, 37-46, 51, 55-56, 60-64]. We will use specialty of the first physician (urologist, urologic oncologist, oncologist, radiation oncologist) who the patient saw during PCa diagnosis as an IV. We will explore other potential IVs, such as absolute distance between patients residence to the hospital where they will receive care (Hospital of University of Pennsylvania, Presbyterian Medical Center, PVAMC, Pennsylvania Hospital, or Fox-Chase Cancer Center). Validity of the IV(s) is assessed as following. First, we will use Pearsons correlation coefficient to examine the correlation between IV, primary exposure (treatment) and outcomes. We will then perform a partial F-test using a linear regression where treatment group is regressed on physician specialty along with patient attributes. For a valid IV, test statistic should be very high (e.g., physician specialty will strongly predict treatment after adjusting for covariates). Next, we will perform a partial F-test using a linear probability model in which HRQoL outcomes are regressed on specialty and patient demographic and clinical variables. For an IV to be valid, this test statistic should be very low. Finally, we will compare observable attributes across patient groups cared for by different physician specialty (initial). For the IV be valid, these groups should have comparable observable attributes. **Phase 1 Focus group analysis-development of conjoint task instrument:** The goal of focus groups is to identify attributes of PCa treatment that are most salient to localized PCa patients. This process includes following steps: (1) identifying and defining attributes; (2) assigning attribute levels; and (3) creating scenarios and choice sets. Attributes will be defined based on input from patient focus groups, literature, our prior research, and prior physician focus group. Once an attribute and its extreme values are defined, we will assign them appropriate levels. A large number of possible combinations of attributes and levels will preclude

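### The instrument-validity rule demands no link between specialty and HRQoL in a model without treatment, so it tends to reject valid instruments and a pass proves nothing

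*Combined protocol and SAP*

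**What the plan says.** Under Analysis Plan, Instrumental variable analysis, the plan defines the method: "This technique uses one or more observable factors that influence outcome only indirectly (the IV". The main instrument is the "specialty of the first physician (urologist, urologic oncologist, oncologist, radiation oncologist) who the patient saw during PCa diagnosis as an IV", a four-level variable. Distance from home to hospital is mentioned as another candidate.

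After looking at simple correlations, the plan sets three validity criteria:

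1. Treatment is regressed on specialty and patient attributes: "For a valid IV, test statistic should be very high".
2. For the outcome, "we will perform a partial F-test using a linear probability model in which HRQoL outcomes are regressed on specialty and patient demographic and clinical variables". The criterion is: "For an IV to be valid, this test statistic should be very low".
3. Patients are compared across specialties: "For the IV be valid, these groups should have comparable observable attributes".

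No numerical cut-off is given for criterion 2, and no action is stated if an instrument fails. The general paragraph of the Analysis Plan places the method inside each randomised arm, as an "instrumental variable approach to minimize observed and unobserved bias within groups (i.e. intervention group and usual care control group".

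**The concern.** Criteria 1 and 2 conflict. Treatment is not listed in the outcome regression, and the potential confounding variables in section D.2.4.4 (severity, Gleason score, comorbidity, demographics) do not include it. The specialty coefficient therefore carries everything that specialty does to HRQoL through treatment. On the plan's own definition that indirect path is how an instrument works, and Background section A.6.2 says that HRQoL differs across treatments. A strong and valid instrument should then be associated with HRQoL.

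Two errors follow. Good instruments tend to be rejected, and more often the stronger they are and the larger the treatment effect. A low F may also be reported as evidence of validity when it reflects no treatment effect, low power, or a direct effect that offsets the indirect one. This matters because the IV analysis is the only method the Analysis Plan names for unobserved bias in comparisons by treatment received.

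**Working it through.** The plan gives no figure for this check, so there is none to reproduce.

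**Algebra.** Let specialty Z shift treatment D by π, let treatment shift HRQoL by β, and let δ be any direct effect of Z on HRQoL. With D left out, the coefficient of Z is πβ + δ. Validity requires δ = 0. The rule asks for πβ + δ ≈ 0. With π large (criterion 1) and β ≠ 0, a valid instrument gives πβ ≠ 0.

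**Inputs from the plan.** 360 men per arm (Study Design); 7 points as a clinically meaningful SF difference and SDs of 8 to 14 (Accrual).

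**Assumptions.** Binary treatment; binary instrument split 180/180; low means p≥0.05; failing instruments are not used; unmeasured confounding c between −0.5 and +0.5, where c is the correlation of the confounder with the outcome error.

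**Approximate calculation, SD 14.** The standard error of the difference between instrument groups is 14 × √(2/180) = 1.48.

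- π = 0.39 (first-stage F about 67): πβ = 0.39 × 7 = 2.73 and z = 2.73/1.48 = 1.85. The chance of p≥0.05 is about Φ(1.96 − 1.85) = 54%.
- π = 0.22 (F about 20): z = 1.54/1.48 = 1.04, kept about 82%.
- π = 0.55 (F about 162): z = 3.85/1.48 = 2.61, kept about 26%.

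Simulation (4,000 replicates per case) over the range of c agrees:

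| Case | Kept | Median retained estimate (truth 7) |
|---|---|---|
| Valid, F about 20 | 81–85% | 5.4–5.7 |
| Valid, F about 67 | 50–60% | 4.6–4.9 |
| Valid, F about 162 | 23–31% | 3.8–4.2 |
| Valid, F about 67, SD 8 | 8–21% | 3.4–4.2 |
| Invalid, δ = −2, F about 67 | 92% | 1.5–1.6 |

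Without the screen, the median estimate from the valid instruments at SD 14 is 6.8–7.1. With a true effect of zero, a valid instrument is kept 95% of the time.

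**Why retained estimates shrink.** An instrument is kept only if the difference is below about 1.96 × 1.48 = 2.90 points. With π = 0.55 the IV estimate is then capped near 2.90/0.55 = 5.3, below the true 7.

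**Why the invalid instrument passes.** Its net effect is 2.73 − 2 = 0.73 points, z = 0.73/1.48 = 0.49, kept about 92%. Its IV estimate centres near 0.73/0.39 = 1.9.

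**Four-level specialty (3-df test).** At F about 21 and 51, a valid instrument is kept 70–76% and 40–51% of the time, with median retained estimates of 5.5–6.0 and 4.8–5.4.

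**If treatment was meant to be in the model.** Conditioning on treatment, which both the instrument and the unmeasured confounders affect, links those two. At F about 67, a valid instrument is kept 46% of the time with median 9.6 at c = +0.5, and 45% with median 4.4 at c = −0.5. The bias can go either way.

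**The case against.** The algebra is not in dispute. The case on the other side is about size and importance.

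- **The illustration can be made milder.** The plan's regression is a linear probability model, which suggests a binary outcome. Splitting HRQoL near its median raises the kept shares to about 85–86%, 65–66% and 41%. A pairwise treatment contrast within an arm would have about 120 men (60 per treatment), and the shares are then about 91–92%, 80–83% and 65–70%. With first-stage F about 5–6 at n=360, about 92% are kept. This stands. Rejection is frequent only for strong instruments with reasonable numbers, so the right wording is that the rule tends to reject them. But strong instruments are what criterion 1 asks for.
- **The rule catches some invalid instruments.** With a direct effect of +2 points, it rejects about 84–91% of runs, against 40–50% for the valid instrument. True, but it does so only when the direct effect adds to the indirect one.
- **The plan does not say that failing instruments are dropped.** Also true. The bias figures depend on that assumption; the misreading of a low F as validity does not.
- **Baseline HRQoL may have been meant.** That would be a legitimate check, but the text says outcomes and names no time point.
- **The analysis is peripheral.** The aim-specific sections do not name it. That limits the scope, but does not make the rule correct.

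**Conclusion.** The concern holds. As written, criterion 2 tests the reduced form, conflicts with criterion 1 whenever treatment affects HRQoL, and cannot establish validity. With 360 men, a 7-point effect and SD 14, it would discard a valid binary instrument about 15–19% of the time at first-stage F about 20, and 69–77% at F about 162. A partly cancelling invalid instrument would be accepted 92% of the time. These figures are illustrative. They rest on the assumed cut-off of p≥0.05, a binary treatment, and assumed instrument strength and confounding. The pull of retained estimates towards zero further assumes that failing instruments are not used. The damage is confined to the non-randomised comparisons by treatment received; the Aim 3 intent-to-treat comparison is unaffected. It should be fixed before the analysis is run.

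**What to change.** Amend the Instrumental variable analysis text as follows:

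1. Delete the requirement of a low outcome F.
2. Keep the first-stage partial F and the covariate comparison.
3. Report the association of specialty with follow-up HRQoL as part of the IV result, not as a screen.
4. Add a falsification check: regress baseline SF-36 and EPIC scores on specialty and the same covariates, and report differences with 95% confidence intervals and no pass/fail rule.

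The text should state the limits of the new check:

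- It detects only imbalance that shows in baseline HRQoL, not a direct effect of specialty on later HRQoL.
- Timing is not fully settled. Under Procedures, "participants will receive the following surveys via mail within 1-2 weeks after enrollment and prior to treatment initiation: SF-36, EPIC", which allows completion after the treatment decision, while the recruitment text has the intervention arm complete its surveys before deciding. If the decision itself moved a score by 2 or 4 points, a valid instrument with π = 0.39 would show a baseline difference of about 0.8 or 1.6 points.
- Power is modest. For a 4-point maximum difference across four equal specialties (SD 14, 3-df test), the noncentrality is n × variance of the means / 14². At n=360 this is 4.08, 5.51 or 7.35 for evenly spread means, one differing, or two against two, giving power of 36%, 48% or 61%. With the arms pooled (n=720), power is 66%, 80% or 91%. With assumed specialty shares of 60/20/5/15%, it is 14–59% (n=360) or 26–90% (n=720).
- The unadjusted 95% half-width between two specialties of 90 men is 1.96 × 14 × √(2/90) = 4.1 points, or 2.9 with arms pooled.

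The cost is a wording change. The baseline scores are already collected, and no study procedure changes.

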patients in decision (measured using CPS) using multi-nominal regression model to adjust for observed covariates. Then we will examine if these associations vary across intervention and usual care control groups. We then will repeat the model with other independent variables (decision conflict and trust). Next, we will test the association denoted by path c (direct effect of DCS, CPS, and trust on outcomes). For continuous outcomes (HRQoL, AUA-SI, MAX-PC, CES-D, SWD, and PSQ-18), we will compute area under the curve (AUC) for each measure for each patient. We will analyze AUC summaries with univariate linear models. In our main analysis we will analyze the series of functional status measures using linear mixed models that predict the outcome from time, independent variables and their interaction. We will repeat the analyses described for path c, this time by including treatment received in the models. We will test if the observed effects of DCS, CPS or trust on outcomes will be weaker after controlling for treatment. These analyses will be performed within and between groups (intervention and usual care controls). Specific Aim 3: Hypothesis: Prostate cancer patients in the intervention group undergoing conjoint analysis-value clarification exhibit improved treatment choice, satisfaction with decision, lower regrets, and improved objective and subjective outcomes. Analysis for Specific Aim 3 uses intent-to-treat approach: all randomized participants will be included regardless of whether they drop out of the intervention or study. Analysis will involve comparison of the primary outcomes between intervention and usual care control groups. Improved treatment choice is operationalized as the likelihood of low-risk PCa patients receiving active surveillance than active treatment, and will be compared between intervention and usual care control group. To allow for different trajectories of the outcome measures and to afford flexibility in making contrasts within participants over time and across participants, while simultaneously controlling for potential confounders, we propose the participant-specific or mixed effects linear model, in which the mean outcome depends on fixed covariates and random effects. The primary fixed effects will be indicators for intervention group and hospital. We will also stratify the analysis by type of treatment. The random effects represent the unobserved factors that lead to variation of the individual participants outcome. Random intercepts for each participant permit modeling of natural variation across participants at baseline. In addition, random slopes or random effects for the trajectory of each participant over time, allow for variation of each participant about a mean, overall trajectory across all participants. Although less robust to model misspecification, the mixed effects paradigm offers special flexibility in longitudinal data when exposures vary over time and when dropout and missed visits lead to unbalanced groups. The target of inference is the participant-specific response to treatment over time. At each time point of interest, we will estimate from the fitted model the difference from baseline in outcome for the treatment and control groups and test the difference between these differences. Both univariate and multivariate results will be reported in terms of Wald test, point estimates, and 95% confidence intervals. Specific Aim 4: Hypothesis 4: Prostate cancer patients whose treatment is more concordant with their values markers will experience improved subjective and objective outcomes. This specific aim s for intervention group only. We will analyze the association of the concordance between stated individual preferences and actual treatment received with objective (PCa recurrence and complications), subjective (HRQoL, psychological wellbeing, SWD, and satisfaction with care) outcomes, across treatment groups, adjusting for covariates. Association between the value markers (profiles) and measures of outcomes and personal and clinical characteristics: The value markers will be studied for their relationship with socio-demographic and clinical characteristics. We will also assess the association of value markers with outcomes. We will perform logistic regression with outcomes as the dependent variable and dummy variables for the utility-based profiles obtained earlier as independent variables. We will perform this evaluation with and without adjusting for patient attributes in the logistic model. For each case (adjusting and not adjusting for patient attributes), the evaluation of association between these profiles and outcomes will be based on a likelihood ratio test of the set of odds ratios corresponding to the dummy variables of the profiles. Additionally, we will perform a sequence of pair wise tests of comparisons of the profiles in terms of the proportion of type of treatment received based on the Holms multiple comparisons approach. This procedure is hierarchical in that it will identify the utility-based profile at the start of the process before making other comparisons, thus protecting the Type I error from additional comparisons. Specifically, Holms approach tests each pair-wise comparison in ascending order of p-values. Successively larger p-values have less rigorous alpha. The sequential Holm tests terminate after the first non-significant comparison so no subsequent comparison is significance. Concordance and its assessment: Understanding and respect for the patients preference and values is the main aspect of concordance [69, 73]. Thus a first step in concordance involves the physician extracting and understanding the patients view, followed by an agreement between the physician and patient regarding a management plan that integrates their views. There exist many definitions of concordance. For the purpose of this study, we operationalized concordance as agreement between a patients value markers and the attributes (or characteristics) of the treatment that

the patient receives (choice). Association of concordance between stated preference and attributes of treatment received will be studied separately for each treatment using Kappa statistics. The degree of concordance then will be used as an independent variable to test its association with outcomes. For objective/clinical outcomes (i.e., complications and PCa recurrence), we will test the hypothesis that degree of concordance is associated with PCa recurrence (measured by PSA doubling time). To evaluate the effects of concordance on biochemical recurrence of PCa, we will analyze PSA levels on the log scale over time using a mixed model approach. We also will apply survival analyses (Kaplan-Meier, logrank and Cox model) to model effects concordance of treatment and covariates on time to PSA recurrence. For subjective outcomes of urologic symptoms (AUA-SI), generic and prostate specific HRQoL, psychological well-being (CES-D, MAX-PC), satisfaction with decision and satisfaction with care, we will perform inferential analysis with t, chi-squared and non-parametric tests. Wilcoxon matched-pairs test will be used for comparisons within concordance and non-concordance groups. A concordance group will be defined as at least 75% agreement between values markers and treatment related attributes. We will perform sensitivity analysis to test robustness of results. Primary analyses will compare baseline with six and 24 months assessments, as literature suggests these are the clinically most relevant time points. Secondary analyses will compare baseline with three month and one year outcomes. Proportion returning to baseline over time will be compared using chi-squared tests, using procedures such as Bonferroni, Scheffé, and step-down Holm corrections to adjust for multiple testing. We will use loglinear regression models with psychological well being, HRQoL and satisfaction with care scores (log) as dependent variables, logistic regression with return to baseline as the dependent variable, and degree of concordance as the independent variable. For repeated measures outcomes we will use linear mixed models (Proc Mixed).

The following documents are currently attached to this item:

There are no documents attached for this item.

Deception

Does your project use deception?

No

Data confidentiality

- x Paper-based records will be kept in a secure location and only be accessible to personnel involved in the study.**
- x Computer-based files will only be made available to personnel involved in the study through the use of access privileges and passwords.**
- x Prior to access to any study-related information, personnel will be required to sign statements agreeing to protect the security and confidentiality of identifiable information.**
- x Wherever feasible, identifiers will be removed from study-related information.**

A Certificate of Confidentiality will be obtained, because the research could place the subject at risk of criminal or civil liability or cause damage to the subject's financial standing, employability, or liability.

A waiver of documentation of consent is being requested, because the only link between the subject and the study would be the consent document and the primary risk is a breach of confidentiality. (This is not an option for FDA-regulated research.)

- x Precautions are in place to ensure the data is secure by using passwords and encryption, because the research involves web-based surveys.**
- x Audio and/or video recordings will be transcribed and then destroyed to eliminate audible identification of subjects.**

Subject Confidentiality

Protection of Participants and Procedure of Protection of Confidentiality: We will institute strict procedures to maintain confidentiality and will adhere to 2003 HIPAA Standards for Privacy of Individually Identifiable Health Information (the Privacy Rule). Blood draw will be conducted at the Outpatient clinic, which, as a geriatric outpatient clinic, is a very safe setting for any medical tests. All information on participants will be maintained confidentially, and will be shared with collaborating institutions and PCORI only by means of code. The patients physician will have the right to know of the

patients participation in this study, and may be informed of which group the patient is in if the patient chooses or if there is a medical reason to necessitate this. The research coordinator will meet with the participants at the urology and radiation oncology clinics, and the participant will know whom to contact in case of emergency. Release of participant information to other parties not affiliated with the research team will be governed by the HIPAA Privacy Rule Guidelines. Disposition of data: The raw data will be stripped of participant identifiers immediately and each participant will be assigned a unique identifier. Our unique participant identifier is a number that is incremented by one for each new consented participant accrued in the study. This identifier number is not derived or linked to the participants social security number, hospital ID number, medical record number, or some other number that can also be used to directly identify the data source. The participant identifier information will be held highly confidential and only the principal investigator will have access to it. The principal investigator will maintain a master file linking the participants medical record number and the assigned unique participant identifier. This file will be password protected on a secured computer. The data will be stored on a secure and password protected computer. Every attempt will be made by the investigators to maintain all information collected in this study strictly confidential. In any publications or presentations resulting from this research, data will be presented in aggregate format only and the participants will not be identified individually. To ensure accuracy of data while transferring raw data to computerized database, data will be verified in three steps. First, double entry will be done for raw data that are entered into a computer. Next, the principal investigator will perform a random data check. Finally a one-way frequency of all the variables will be run and checked to see if any incorrect or out of range information appears in the database. If so, the necessary corrections will be made. In order to generate the final report and publications, data will be stored for approximately four years beyond the end of the study period. Sharing Study Results: We will seek advice from institutional review and data safety monitoring board regarding sharing the study results with participants over the study duration. The published results will be made available to all the participants, caregivers and physicians. Ethical Considerations: This study will not modify a participants prescribed medical regimen in any way. The major ethical considerations involve issues of notification of physicians when participants are worsening. Since our research coordinator and research assistant are not medical practitioners, their role will be to remind the participant that they must take action if their condition is worsening (e.g. notify the physician). The research coordinator will be given guidelines by the medical co-investigators to identify extreme cases. In these instances, the investigators will contact the participants physician.

Sensitive Research Information*

Does this research involve collection of sensitive information about the subjects that should be excluded from the electronic medical record?

No

Subject Privacy

Privacy refers to the person's desire to control access of others to themselves. Privacy concerns people, whereas confidentiality concerns data. Describe the strategies to protect privacy giving consideration to the following: The degree to which privacy can be expected in the proposed research and the safeguards that will be put into place to respect those boundaries. The methods used to identify and contact potential participants. The settings in which an individual will be interacting with an investigator. The privacy guidelines developed by relevant professions, professional associations and scholarly disciplines (e.g., psychiatry, genetic counseling, oral history, anthropology, psychology).

Protection of Participants and Procedure of Protection of Confidentiality: We will institute strict procedures to maintain confidentiality and will adhere to 2003 HIPAA Standards for Privacy of Individually Identifiable Health Information (the Privacy Rule). Blood draw will be conducted at the Outpatient clinic, which, as a geriatric outpatient clinic, is a very safe setting for any medical tests. All information on participants will be maintained confidentially, and will be shared with collaborating institutions and PCORI only by means of code. The patients physician will have the right to know of the patients participation in this study, and may be informed of which group the patient is in if the patient chooses or if there is a medical reason to necessitate this. The research coordinator will meet with the participants at the urology and radiation oncology clinics, and the participant will know whom to contact in case of emergency. Release of participant information to other parties not affiliated with the research team will be governed by the HIPAA Privacy Rule Guidelines. 2.6.7 Disposition of data: The raw data will be stripped of participant identifiers immediately and each participant will be assigned a unique identifier. Our unique participant identifier is a number that is incremented by one for each new consented participant accrued in the study. This identifier number is not derived or linked to the participants social security number, hospital ID number, medical record number, or some other number

that can also be used to directly identify the data source. The participant identifier information will be held highly confidential and only the principal investigator will have access to it. The principal investigator will maintain a master file linking the participants medical record number and the assigned unique participant identifier. This file will be password protected on a secured computer. The data will be stored on a secure and password protected computer. Every attempt will be made by the investigators to maintain all information collected in this study strictly confidential. In any publications or presentations resulting from this research, data will be presented in aggregate format only and the participants will not be identified individually. To ensure accuracy of data while transferring raw data to computerized database, data will be verified in three steps. First, double entry will be done for raw data that are entered into a computer. Next, the principal investigator will perform a random data check. Finally a one-way frequency of all the variables will be run and checked to see if any incorrect or out of range information appears in the database. If so, the necessary corrections will be made. In order to generate the final report and publications, data will be stored for approximately four years beyond the end of the study period. Sharing Study Results: We will seek advice from institutional review and data safety monitoring board regarding sharing the study results with participants over the study duration. The published results will be made available to all the participants, caregivers and physicians. Ethical Considerations: This study will not modify a participants prescribed medical regimen in any way. The major ethical considerations involve issues of notification of physicians when participants are worsening. Since our research coordinator and research assistant are not medical practitioners, their role will be to remind the participant that they must take action if their condition is worsening (e.g. notify the physician). The research coordinator will be given guidelines by the medical co-investigators to identify extreme cases. In these instances, the investigators will contact the participants physician.

Data Disclosure

Will the data be disclosed to anyone who is not listed under Personnel?

NA

Data Protection*

- Name**
- Street address, city, county, precinct, zip code, and equivalent geocodes**
- All elements of dates (except year) for dates directly related to an individual and all ages over 89**
- Telephone and fax number**
- Electronic mail addresses**
- Social security numbers**
- Medical record numbers**
- Health plan ID numbers**
- Account numbers**
- Certificate/license numbers**
- Vehicle identifiers and serial numbers, including license plate numbers**
- Device identifiers/serial numbers**
- Web addresses (URLs)**
- Internet IP addresses**
- Biometric identifiers, incl. finger and voice prints**
- Full face photographic images and any comparable images**
- Any other unique identifying number, characteristic, or code**
- None**

Tissue Specimens Obtained as Part of Research*

Are Tissue Specimens being obtained for research?

No

Tissue Specimens - Collected during regular care*

Will tissue specimens be collected during regulator clinical care (for treatment or diagnosis)?

No

Tissue Specimens - otherwise discarded*

Would specimens otherwise be discarded?

No

Tissue Specimens - publicly available*

Will tissue specimens be publicly available?

No

Tissue Specimens - Collected as part of research protocol*

Will tissue specimens be collected as part of the research protocol?

No

Tissue Specimens - Banking of blood, tissue etc. for future use*

Does research involve banking of blood, tissue, etc. for future use?

No

Genetic testing

If genetic testing is involved, describe the nature of the tests, including if the testing is predictive or exploratory in nature. If predictive, please describe plan for disclosing results to subjects and provision of genetic counseling. Describe how subject confidentiality will be protected Note: If no genetic testing is to be obtained, write: "Not applicable."

Not applicable

Consent

1. Consent Process

Overview

